	Severe Bleeding (EXCLUDED FROM THIS PROTOCOL): (arterial, venous, or mixed) that is rapidly flowing, pulsatile or spurting that in the surgeon's judgment requires rapid control to prevent haemodynamic consequences (e.g. hypovolemia, tachycardia, or hypotension) and could involve major volume loss which if not treated rapidly could be life threatening. EVICEL® should not be used in place of sutures or other forms of mechanical ligation for the treatment of major arterial bleeding.
PROCEDURE:	The TBS will be identified during the dissection (soft tissue or parenchymal organ) related to the primary operative procedure. This will be the site assessed for haemostatic effectiveness.

EudraCT Number: 2013-003401-26

Amendment 4: 08 January 2018

Once the TBS is identified, the surgeon will immediately randomize the subject into the study. The randomly assigned treatment (EVICEL® or SURGICEL®) will be applied immediately at the actively bleeding TBS.

Randomized Subjects

After placement of the assigned study treatment (EVICEL® or SURGICEL®), there will be an observation period during which the TBS will be assessed at 4, 7 and 10 minutes from randomization. SURGICEL® must not be lifted or disturbed when assessing for haemostasis.

- Time to Hemostasis (TTH), from the time of randomization, is recorded once Haemostasis is achieved. Haemostasis will be defined as no detectable bleeding from the TBS at any time point.
- If haemostasis is achieved before four minutes (<4 mins), between four and seven minutes (>4 and <7 mins), seven and ten minutes (>7 and 10< mins) or after 10 minutes, the absolute time to haemostasis must be recorded.
- In the event of bleeding at the TBS during the ten-minute observational period (in either treatment or control group) that requires further haemostatic measures other than re-application of the assigned haemostatic adjunct (EVICEL® or SURGICEL®), the surgeon should perform these measures, and record the subject as a treatment failure for the endpoint "Incidence of treatment failures".
- If re-bleeding occurs at the TBS after haemostasis has been achieved, any rebleeding should be treated by the randomised study product, if clinically appropriate or per the surgeon's standard of care. This should be recorded as an adverse event.

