7.1.3.4 Haemostasis Assessment

After placement of the assigned study treatment (EVICEL® or SURGICEL®), there will be an observation period during which the TBS will be assessed at 4, 7 and 10 minutes from randomization and for absolute time for haemostasis. **SURGICEL® must not be lifted or disturbed when assessing for haemostasis.** Once haemostasis has been achieved, excess SURGICEL may be removed according to the IFU assuring that the clot is not disturbed to avoid potential rebleeding. For additional details consult the IFU Contraindications, Warnings and Precautions sections.

EudraCT Number: 2013-003401-26 Page 20 of 35

CONFIDENTIAL

Protocol: 400-12-006 Amendment 4: 08 January 2018

• Absolute time to haemostasis (TTH from the time of randomization) is recorded once haemostasis

	is achieved. Haemostasis will be defined as no detectable bleeding from the TBS.	
•	Haemostasis is also assessed at the specified time-points (4 7 and 10 minutes following	

•	Haemostasis	İS	also	assessed	at	the	specified	time-points	(4,	7	and	10	minutes	following
	randomizatio	n),	which	h is outline	ed ii	n the	following	timetable:						

T ₀	Start time when randomization envelope is opened
T _{APP}	Time when randomised haemostatic product (EVICEL® or SURGICEL®) is initially applied
T ₄	TBS Bleeding assessment 4 minutes following randomization.
T ₇	Bleeding is assessed 7 minutes after randomization
T ₁₀	Bleeding is assessed 10 minutes after randomization
T _{ABS}	Exact time when absolute haemostasis has been achieved

If haemostasis is achieved before four minutes (<4 min.) after randomization, the absolute time to haemostasis must be recorded.

- If haemostasis is achieved between four and seven minutes (>4 and <7 min.) after randomization, the absolute time to haemostasis must be recorded.
- If haemostasis is achieved between 7 and ten minutes (>7 and <10 min.) after randomization, the absolute time to haemostasis must be recorded.
- If haemostasis is achieved after 10 minutes, this absolute time to haemostasis must be recorded.

Haemostasis Scenarios

- If breakthrough bleeding occurs at the TBS during the 10-minute treatment period, the surgeon may re-treat with the randomised study product, if clinically appropriate. If the subject is randomised to EVICEL®, re-treatment must be performed according to the Investigator Brochure.

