#### 3. STUDY ENDPOINTS

The primary effectiveness endpoint is the absolute time to hemostasis (elapsed from randomization), defined as the absolute time when there is no detectable bleeding at the Target Bleeding Site (TBS).

In addition, the following secondary endpoints will be included in this study:

- Haemostasis at 4, 7 and 10 minutes following randomization;
- Incidence of treatment failures (defined as haemostasis not achieved within 10 minutes or bleeding at the TBS during the ten-minute observational period that requires further hemostatic measures, other than re-application of the assigned hemostatic adjunct);
- Incidence of adverse events (including thrombotic events and events associated with TBS rebleeding);
- Proportion of subjects with no re-bleeding;
- Haemoglobin, Haematocrit, Platelets, Volume of blood loss, Volume of blood and blood products transfusions

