#### 7. PROCEDURE DATA

Procedure data will be summarized descriptively for subjects in each treatment group in the FAS set. The categorical data will be summarized descriptively by frequencies along with the associated percentages. The continuous data will be presented using summary statistics such as number of subjects, mean, standard deviation, minimum, median and maximum.

The following procedure variables will be analyzed:

- Primary operative procedure;
- Operating room (OR) time;
- Procedure duration (from first incision to closure completion);
- Procedure duration from first incision to initiation of final fascial closure (when applicable);
- Specification of treatment to which subject is randomized;
- TBS length, width, area, and location, type of bleeding, and TBS tissue or parenchymal organ type;

Page 5 of 18

Version: AMENDMENT 1 Date: July 1, 2019

- Estimated intraoperative blood loss, blood or blood product transfusions from surgery through hospital discharge, and cell saver usage data;
- Primary method used to obtain hemostasis at the TBS;
- Surgical approach;
- For patients treated with EVICEL, approximate amount of EVICEL used (up to 10 minutes following randomization), number of EVICEL kits used, quantity per kit; in addition, for all EVICEL kit used type of tip, method of application, and size of kit;
- For patients treated with SURGICEL, number of kits used, indication of SURGICEL use according to IFU, approximated SURGICEL length and width used at the TBS, and SURGICEL area applied;
- Hemostasis assessment data, such as time from randomization to initial application of randomized hemostatic product, TBS hemostasis presence at 4, 7, and 10 minutes from randomization, absolute time to hemostasis (from randomization), and presence of any bleeding at TBS between 4 and 10 minutes following randomization;
- Bleeding/durability data, such as indication of any additional treatment use at the TBS, indication of any rebleeding, and, for all rebleeds treatment used for rebleed;
- Length of subject hospital stay (from hospital admission to hospital discharge, as well as from procedure to hospital discharge);
- Time from screening visit to hospital admission, time from baseline visit to hospital admission, time from screening visit to surgery, and time from baseline visit to surgery.

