### 8.3 Secondary effectiveness analysis

The following secondary effectiveness endpoints will be summarized descriptively by treatment group for the FAS:

- Haemostasis at 4 minutes following randomization;
- Haemostasis at 7 minutes following randomization;
- Haemostasis at 10 minutes following randomization;
- Incidence of treatment failures (defined as haemostasis not achieved within 10 minutes or bleeding at the TBS during the ten-minute observational period that requires further hemostatic measures, other than re-application of the assigned hemostatic adjunct).

Two-sided 95% CIs for the proportions of subjects with hemostasis at 4 minutes, 7 minutes, and 10 minutes, will be constructed for each treatment group separately ( $P_E$  for EVICEL and  $P_C$  for Control), using the Clopper-Pearson method. In addition, for each time point, a two-sided 95% CI will be reported for the ratio proportion of successes (hemostasis achieved) in the EVICEL group/proportion of successes in Control group ( $P_E/P_C$ ), using the Farrington-Manning score method.

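### The primary time to haemostasis has no rule for re-bleeding inside the 10-minute window, so T_ABS can mean either the first or the lasting cessation

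*Protocol*

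**What the plan says.** **Primary time.** The protocol synopsis states "Time to Hemostasis (TTH), from the time of randomization, is recorded once Haemostasis is achieved". Section 7.1.3.4 has the same instruction, "Absolute time to haemostasis (TTH from the time of randomization) is recorded once haemostasis" is achieved, and for the earliest interval adds "If haemostasis is achieved before four minutes (<4 min.) after randomization, the absolute time to haemostasis must be recorded". Its timetable has one entry for the primary time, T_ABS: "Exact time when absolute haemostasis has been achieved". SAP 3 and 8.2 repeat the endpoint as time from randomization to no detectable bleeding at the target bleeding site (TBS). No section requires haemostasis to last for any period.

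**Re-bleeding in the window.** Section 7.1.3.4 provides for breakthrough bleeding during the 10 minutes, when "the surgeon may re-treat with the randomised study product, if clinically appropriate". It gives no instruction for T_ABS in that case.

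**Treatment failure.** SAP 8.3 has "Incidence of treatment failures (defined as haemostasis not achieved within 10 minutes or bleeding at the TBS during the ten-minute observational period", the second limb being limited to bleeding that needs some measure other than re-applying the assigned product. Re-application alone is therefore not a failure. Protocol 7.1.3.4 words the first limb differently, by reference to the end of the observation period.

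**Other bleeding data.** SAP 7 lists "presence of any bleeding at TBS between 4 and 10 minutes following randomization", additional treatment at the TBS, and any re-bleeding. SAP 8.3 reports haemostasis at 4, 7 and 10 minutes. SAP 9.1 reports the proportion with no re-bleeding. Protocol 7.1.3.4 records the time and method of each re-treatment.

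**The concern.** The plan foresees that a site may stop bleeding, start again and be re-treated within 10 minutes, but has no rule for the primary endpoint when that happens. If the first stop is kept, a brief pause scores as fast haemostasis and can sit beside a failure at 7 or 10 minutes in the same child. If some sites enter the first stop and others the last, two different variables are pooled under one name.

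The surgeon knows the assignment (Protocol 5), and there are only about 20 children per arm (Protocol 8.1). The medians and their confidence intervals are the whole primary result. If breakthrough bleeding differs between products, the reading chosen changes how the arms compare.

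The point is confined to re-bleeding treated with the assigned product. Rescue with another measure is a separate matter.

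**Working it through.** **1. The two readings applied to two invented cases**

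Case A: dry at 2 min, bleeding again from 5 min, re-treated with the assigned product, dry from 9 min. Case B: dry at 3 min, bleeding again at 9.5 min and still bleeding at 10 min, no other measure used before 10 min.

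| | Case A | Case B |
|---|---|---|
| T_ABS, first cessation | 2 min | 3 min |
| T_ABS, lasting cessation | 9 min | after 10 min |
| Dry at 4 / 7 / 10 min | yes / no / yes | yes / yes / no |
| Treatment failure | no | depends on which wording is used |

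In case A the primary value differs by 9 − 2 = 7 min. With the first stop, 2 min stands beside a failure at 7 min. SAP Table 14.1.3.6 would carry both. In case B, the wording in Protocol 8.3.1, SAP 3 and SAP 8.3 (not achieved within 10 minutes) can be read as satisfied by the dry spell at 3 min. Protocol 7.1.3.4 (not achieved by the end of the period) is more naturally read as status at 10 min.

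**2. Can the lasting time be recovered from other data?**

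- Bleeding between 4 and 10 minutes is a discrete item. It carries no time and misses re-bleeding before 4 min.
- Status at 4, 7 and 10 minutes brackets a second cessation but does not date it.
- The time of re-treatment is when the product was applied, not when bleeding stopped.
- The proportion with no re-bleeding is one yes/no item per child. Whether in-window breakthrough counts is not stated. The synopsis makes any re-bleeding after haemostasis an adverse event, whereas 7.1.3.4 says so only for re-bleeding after 10 minutes. These need to be reconciled.
- SAP 10.2.1 mentions a sensitivity analysis summary for the primary endpoint, but the SAP defines none.

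No section requires the second cessation time.

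**3. Size**

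The documents give no re-bleed rate, spread or effect size, so there is no plan figure to reproduce beyond 20 + 20 = 40. With n = 20, the distribution-free 95% interval for the median runs from the 6th to the 15th ordered value (exact coverage 95.86%). Both scenarios below rest on assumptions.

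*Scenario 1, upper end.* First-stop times are log-normal with median 3 min and log-SD 0.6. A fraction f re-bleeds, unrelated to first-stop time, and is finally dry at 6 to 10 min, so every re-bleeder lies above the median. The lasting median m solves (1 − f)·F(m) = 0.5, where F is the first-stop distribution. Hence m = 3·exp(0.6·z), with z the normal quantile at 0.5/(1 − f).

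| f | 0.5/(1 − f) | z | m (min) | shift from 3.0 |
|---|---|---|---|---|
| 5% | 0.526 | 0.066 | 3.12 | 0.12 |
| 10% | 0.556 | 0.140 | 3.26 | 0.26 |
| 20% | 0.625 | 0.319 | 3.63 | 0.63 |
| 30% | 0.714 | 0.566 | 4.21 | 1.21 |

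These are population medians. Simulated sample medians at n = 20 average slightly higher: about 3.3, 3.8 and 4.4 min at 10%, 20% and 30%, against 3.04 for the first stop.

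*Scenario 2, milder.* First-stop median is 2, 3 or 4 min, log-SD 0.5. Final cessation is uniform between the first stop and 10 min. Results average 40,000 simulated arms of 20.

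| f | median shift (min) | shift in upper CI limit, 15th value (min) |
|---|---|---|
| 5% | 0.07–0.12 | 0.16–0.23 |
| 10% | 0.14–0.24 | 0.36–0.46 |
| 20% | 0.34–0.53 | 0.91–0.99 |
| 30% | 0.61–0.88 | 1.43–1.64 |

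*Unequal arms.* With 10% re-bleeding in one arm and 30% in the other, and equal first-stop times, the recorded first-stop medians would not differ. The lasting medians would differ by 4.21 − 3.26 = 0.95 min in scenario 1. In scenario 2 the gap runs from 0.61 − 0.14 = 0.47 to 0.88 − 0.24 = 0.64 min.

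**The case against.** A reader might infer that the plan stops the clock at the first dry moment and never resets it. The documents do not say that. The sentence in 7.1.3.4 only requires a time to be recorded, T_ABS refers to absolute haemostasis without defining it, and the synopsis definition ends with a phrase about any time point that fits either reading. First cessation is the plainest reading, not a stated rule.

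A reader might also infer that a child bleeding at 10 minutes escapes being a treatment failure. That is no more than an ambiguity, given the wording in 7.1.3.4. The child fails the 10-minute endpoint in any case, and the synopsis makes intra-operative bleeding at the TBS after 10 minutes an adverse event. Nor do the documents say that the surgeon runs the stopwatch, only that the surgeon is unblinded.

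The best defence is that first cessation, with durability reported separately, is a legitimate endpoint, and that a quick first stop followed by failure at 7 minutes is two facts rather than a contradiction. The analysis is descriptive, with no test and no formal sample size, so no pass/fail decision turns on the rule. The SAP does report durability in several places.

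Much of this stands. It limits the consequences and rules out any claim that re-bleeding is hidden. It does not supply the missing rule: a plan that meant first cessation would still have to say so, and the separate summaries cannot turn a first-stop time into a lasting one. The case report form pages are not in the documents, so a second time field may already exist.

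**Conclusion.** The gap is real. The primary endpoint is undefined for a child who re-bleeds within 10 minutes and is re-treated with the assigned product, and the time needed to settle it afterwards is not required to be collected. That rests on the text alone.

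The size rests on assumed re-bleed rates and time distributions. Across the two scenarios the arm median moves by about 0.1 min at 5% re-bleeding, 0.14 to 0.3 min at 10% and 0.6 to 1.2 min at 30%. A between-arm distortion near 1 min needs both unequal re-bleeding (10% against 30%) and the upper-end assumption; the milder one gives about half to two-thirds of that. If re-bleeding is rare the effect on the median is small, though the value for a single child can still be wrong by several minutes.

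**What to change.** 1. In Protocol 7.1.3.4 and SAP 8.2, define T_ABS as the start of the bleed-free period that still holds at the 10-minute assessment, or the first later such time. Re-record it after any re-bleed inside the window. A T_ABS at or before 7 or 10 minutes then guarantees that the site was dry at that assessment. The converse need not hold at 7 minutes, because a site dry then may bleed later.
2. Keep the first cessation in a second eCRF field and summarise it by arm as supportive. This could also be the sensitivity analysis that SAP 10.2.1 mentions without defining.
3. Align the treatment-failure wording in Protocol 8.3.1, SAP 3 and SAP 8.3 with Protocol 7.1.3.4, so that a subject bleeding at 10 minutes is clearly a failure.
4. State whether in-window breakthrough counts in the proportion with no re-bleeding, and reconcile the synopsis with 7.1.3.4 on when re-bleeding is an adverse event.

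The cost is at most one extra time field and a few sentences in each document. No treatment changes. Recorded times become somewhat longer, and so less favourable, in subjects who re-bleed.

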5 RANDOMIZATION

Randomization will be used to avoid bias in the assignment of treatment to each subject, to increase the likelihood that attributes of the subject are evenly balanced across treatment groups, and to enhance the validity of statistical comparisons across treatment groups.

ETHICON will provide each site with computer-generated randomization envelopes, each bearing the subject randomization number, and containing the treatment allocation.

Treatment will be assigned randomly to each subject on a 1:1 basis to either EVICEL® or SURGICEL® treatment.

In the event that a potential subject fails intra-operative criteria (i.e. no TBS identified, or an intra-operative exclusion), and is not randomized to the study, the unused randomization envelope should be returned to the series, and used for the next subject.

Given the difference between the EVICEL® and SURGICEL® treatment groups, it will not be possible for the surgeon to be blinded to the treatment. However, to avoid any bias in the conduct of the surgical procedure, randomization should only take place after completion of the following steps:

- 1. EVICEL® and SURGICEL® will be prepared and available in the sterile field in the operating room, ready for administration for each patient.
- 2. The investigator must perform the surgical procedure according to his/her standard of care.
- 3. Once the investigator encounters an appropriate soft tissue or parenchymal organ TBS related to the primary operative procedure, randomization should immediately take place.

-

⁵ See Appendix 1

Amendment 4: 08 January 2018

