- In the event of bleeding at the TBS during the 10 minute observational period (in either EVICEL® or SURGICEL treatment group) that requires further and immediate haemostatic measures other than re-application of the assigned haemostatic adjunct (EVICEL® or SURGICEL®), the surgeon should perform these measures, and the subject will be a failure for the secondary endpoint "incidence of treatment failures".
- If haemostasis is not achieved by the end of the 10 minute observational period, the surgeon may then apply the use of further haemostatic measures according to his/her preference, and record the subject as a treatment failure.
- If additional soft tissue or parenchymal organ bleeding sites are identified, the surgeon may treat with the same treatment product according to the subject's randomization assignment, if clinically appropriate. Time to haemostasis does not need to be recorded for these additional bleeding sites. However if a subject is randomised to SURGICEL® treatment group, EVICEL® should not be used to treat any other soft tissue bleeding sites. There is no restriction on the use of SURGICEL® in the EVICEL® treatment group to treat other bleeding sites. SURGICEL® must be used per its instructions for use.

EudraCT Number: 2013-003401-26 Page 21 of 35

Amendment 4: 08 January 2018

• If re-bleeding at the TBS occurs after the 10-minute haemostatic assessment period, this can be treated with the randomised study product or the surgeon's standard of care and **must be recorded** as an adverse event.

- Any additional treatments at the TBS at any time during the procedure whether it be the randomized treatment or other clinically appropriate treatments will be recorded, including time and method of retreatment.
- Number of EVICEL® kits used; or Number of SURGICEL® product kits used and standard of care treatments (if applicable) will be recorded.

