8.3.2 Methods of Analysis

Descriptive statistical analysis will be conducted overall and by treatment. Primary endpoint data will also be descriptively summarised into Neonates (birth to 30 days), Infants and toddlers (31 days to <24 months), Children (2 to 11 years) and Adolescent (12 to <18 years). Two-sided 95% confidence intervals (CIs) for median absolute time to hemostasis will be reported separately for EVICEL® and control groups. For the success/failure data (4, 7 and 10 minute hemostasis endpoints), the two-sided 95% CI will be quoted for P_F , P_C and for ratio P_F / P_C , where P_F is the proportion of success in EVICEL® subjects and P_C is the proportion of success in SURGICEL® control subjects. The lower limits of these 95% CI will be utilised for statistical inferences.

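### A subject whose bleeding is stopped by another measure within 10 minutes can count as a success at 7 and 10 minutes, keep a short primary time, and also be a treatment failure

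*Protocol*

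**What the plan says.** - **Haemostasis.** Protocol 7.1.3.4: "Haemostasis will be defined as no detectable bleeding from the TBS". SAP 3 and 8.2 define the primary time by the same test, counted from randomization. SAP 8.3 takes success in P_E/P_C to be haemostasis achieved. None of these asks what stopped the bleeding.
- **Another measure within 10 minutes.** Protocol 7.1.3.4: "the surgeon should perform these measures, and the subject will be a failure for the secondary endpoint" that counts treatment failures. The Synopsis has the same rule: "record the subject as a treatment failure for the endpoint". Only that one endpoint is named.
- **After 10 minutes.** For a subject still bleeding, "the surgeon may then apply the use of further haemostatic measures according to his/her preference". In the same section: "If haemostasis is achieved after 10 minutes, this absolute time to haemostasis must be recorded".
- **Use of the intervals.** SAP 8.3 gives Clopper-Pearson intervals for each arm and a Farrington-Manning interval for P_E/P_C at each time point. Protocol 8.2 and 8.3.2 add: "The lower limits of these 95% CI will be utilised for statistical inferences".
- **Blinding.** Protocol 5: "it will not be possible for the surgeon to be blinded to the treatment".
- **Missing data.** Protocol 8.6 and SAP 8.5.1 do not apply, because a rescued subject has observed data. The full analysis set (FAS) keeps all randomized subjects.
- **Already tabulated.** Table 1.3.6 shows bleeding at the TBS between 4 and 10 minutes, Table 1.3.7 additional treatment at the TBS, and Tables 2.2.4 (FAS) and 3.3 (Safety set) treatment failures.

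**The concern.** The stated objective (Protocol 2) is the haemostatic effectiveness of EVICEL against SURGICEL. If bleeding stopped by a third measure counts as success, the 7- and 10-minute proportions, and the 4-minute one if rescue is very early, describe assigned product plus whatever the surgeon added. The surgeon who decides on rescue knows the allocation.

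Two programmers could treat these subjects differently in Tables 2.2.1 to 2.2.3, and nothing in SAP 8.3 would tell them apart. The stake is the ratio, which is the only between-arm contrast with a planned interval, and to a lesser degree the median time and its upper confidence limit.

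**Working it through.** The plan has no rescue rate, expected haemostasis rate or power calculation, so there is no figure of its own to reproduce. All counts below are assumptions. From the plan: 20 per arm (Protocol 8.1), the Farrington-Manning score interval (SAP 8.3) and the distribution-free interval for the median (SAP 8.2).

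**1. One subject through the rules.** Another measure is used at 5 minutes and the TBS is dry from 6 minutes on.

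| Endpoint | Result as written |
|---|---|
| Primary time | 6 min |
| Haemostasis at 4 min | no |
| Haemostasis at 7 and 10 min | yes |
| Treatment failure | yes |

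The 10-minute success and treatment-failure proportions therefore need not add to 100%. The overlap arises only with rescue inside 10 minutes; a subject still bleeding at 10 minutes is consistently a non-success and a failure.

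**2. The ratio.** The score statistic is z(R) = (p_E − R·p_C) / sqrt[ q_E(1 − q_E)/20 + R²·q_C(1 − q_C)/20 ], where q_E = R·q_C are the proportions fitted under ratio R. The 95% limits are the R at which z = ±1.96. At R = 1 the fitted proportion is the pooled one.

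- Unaided 18/20 v 12/20: pooled 30/40 = 0.75, z = 0.30 / sqrt(2 × 0.75 × 0.25/20) = 0.30/0.137 = 2.19.
- One rescued control counted as a success, 18/20 v 13/20: pooled 31/40 = 0.775, z = 0.25 / sqrt(2 × 0.775 × 0.225/20) = 0.25/0.132 = 1.89.

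Solving for the limits:

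| Unaided E v C | Rescued and counted as success | Unaided ratio (95% CI) | Ratio as written (95% CI) |
|---|---|---|---|
| 18 v 12 | 1 control | 1.50 (1.05–2.36) | 1.38 (0.99–2.11) |
| 18 v 12 | 2 controls | 1.50 (1.05–2.36) | 1.29 (0.93–1.90) |
| 18 v 14 | 1 control | 1.29 (0.93–1.90) | 1.20 (0.88–1.72) |
| 16 v 16 | 3 EVICEL | 1.00 (0.70–1.42) | 1.19 (0.92–1.64) |

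In the first row one subject takes the lower limit below 1. In the third nothing is crossed. In the fourth the shift favours EVICEL.

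**3. Size for one arm.** Against a rule that counts rescue as failure, each rescued subject adds 1/20 = 5 points. Against what would have happened unaided the gain is smaller, because some rescued subjects would have stopped bleeding anyway. A simulation assumed lognormal times with log-SD 0.8, true median 3, 4 or 5 min, the slowest 4 of 20 rescued if still bleeding at a time uniform on 2–6 min, and dryness 0.5 min later. Recorded 10-minute success exceeded the rescue-as-failure rule by 19–20 points, but exceeded unaided success by only 6.5, 11.9 and 16.2 points.

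**4. The median.** At n = 20 the interval runs from the 6th to the 15th ordered time, with coverage 1 − 2·P(Bin(20, 0.5) ≤ 5) = 95.9%. In the same simulation, using recorded times instead of ranking rescued subjects last lowered the median by 0.15–0.87 min for rescue at 2–6 min, 0.00–0.21 min at 4–10 min, and about 0.01 min or less at 7–10 min. With a true median of 5 min, the upper limit fell from 8.2 min to 5.8, 6.9 and 7.6 min respectively.

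**The case against.** **Separate endpoints.** Dry at a given time and needed rescue are coherent separate questions, and the protocol lists them separately. This stands: a reader might infer that the documents contradict themselves, but being a success on one endpoint and a failure on the other is not in itself an error. What is missing is a statement that success counts haemostasis by any means, and a version tied to the assigned product.

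**Already reported.** Tables 1.3.6, 1.3.7, 2.2.4 and 3.3 show much of the picture, and the failure tables largely cover the 10-minute question apart from re-bleeding. This stands in part. Table 2.2.4 specifies no interval for the contrast, the Safety set is descriptive only (SAP 9.4), there is no 4- or 7-minute version, and the primary time is untouched.

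**Thin inference.** No null value or margin is stated. The SAP omits the protocol's sentence on lower limits and calls the evaluation descriptive (SAP 8.2.1). A reader might infer from the first row of the table that one subject could overturn the trial's conclusion; the documents support no such claim, since crossing 1 triggers no stated decision. The protocol's sentence nevertheless remains in force.

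**A sensitivity analysis is promised.** In-text table T3 (SAP 10.2.1) names one, but its sources are only the FAS and per-protocol tables. It may simply mean the per-protocol analysis. The Appendix 1 shells are a separate attachment and were not seen.

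**Conclusion.** The gap is real and worth fixing before analysis. Read literally, both documents count a subject dried by another measure within 10 minutes as a success in P_E/P_C, with an unadjusted primary time.

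The size is unknown because no rescue rate is given. At 20 per arm each such subject moves an arm's proportion by 5 points relative to counting rescue as failure, and by less relative to the unaided outcome. The median moves materially only if rescue is early; its upper limit can move more.

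A reader might infer a bias towards EVICEL, or always towards no difference. Neither follows: the ratio falls if controls are rescued more and rises if EVICEL subjects are. The figures rest on assumed counts, the lognormal shape, and the assumption that the slowest subjects are rescued.

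**What to change.** 1. **SAP 8.3.** Count a subject as a success at 4, 7 or 10 minutes only if there is no detectable bleeding at the TBS at that time and no haemostatic measure other than the assigned product has been used there between randomization and that time. Show the dry-by-any-means version, with the same intervals, beside it.
2. **SAP 8.2.** Keep the recorded-time summary and say that it counts haemostasis by any means. Add one defined sensitivity analysis of the median and its distribution-free interval. In it, rank after all unaided times those subjects whose recorded haemostasis came only after another measure at the TBS, at any clock time, and those whose bleeding was never controlled. Report a quantile as not reached where that applies. Subjects dry on the assigned product who later re-bleed keep their recorded time, and the re-bleed is reported separately.
3. **Protocol 2.** Its treatment-failure definition omits the part about needing another measure. Align it with the Synopsis, Protocol 8.3.1 and 8.4.1, and SAP 3 and 8.3.

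**Cost.** SAP wording, one derivation and a few table rows. The inputs are already collected: Protocol 7.1.3.4 has additional treatments at the TBS logged, and "other clinically appropriate treatments will be recorded, including time and method of retreatment". Clinical management does not change. Single-arm results will look less favourable. In the sensitivity analysis the upper limit, the 15th of 20, is not reached once 6 or more subjects are ranked last (20 − 15 + 1 = 6); small age groups get there sooner.
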